	
 
• Body weight category <math>\geq 50</math> kg: starting dose of 200 <math>\mu\text{g}</math> titrated up to the iMTD or the maximum of 1,600 <math>\mu\text{g}</math> b.i.d.
 
• Body weight category <math>\geq 25</math> to <math>< 50</math> kg: starting dose of 150 <math>\mu\text{g}</math> titrated up to the iMTD or the maximum of 1,200 <math>\mu\text{g}</math> b.i.d.
 
• Body weight category <math>\geq 9</math> to <math>< 25</math> kg: starting dose of 100 <math>\mu\text{g}</math> titrated up to the iMTD or the maximum of 800 <math>\mu\text{g}</math> b.i.d.
 
 
Up-titration will be agreed upon during scheduled telephone calls or visits. At Week 12, the iMTD for each participant will be determined. This dose should be kept unchanged until Week 16. Body weight category, starting dose, and up-titration scheme determined at Baseline/Enrollment will be kept unchanged until Week 16. After Week 16, if the body weight category of the participant has changed, the study drug can be up-titrated further or down-titrated to the corresponding dose level of the next body weight category, if deemed appropriate by the investigator. In addition, irrespective of whether the body weight category changes or not, after Week 16 the investigator will be allowed to change the participant's study drug dose further if needed (up to the maximum allowed dose based on body weight category).
 
If a participant has tolerability issues or experiences adverse reactions reflecting the mode of action for selexipag [see Section 5.1.10], the dose can remain the same without further up-titration (pause in up-titration). Up-titration can be resumed after the pause, or the dose can be reduced to the previous dose level. The decision to pause up-titration, to up-titrate or down-titrate study drug, or to permanently discontinue the study drug will be based on the investigator's medical judgment.

ENDPOINTS	
Primary pharmacokinetics endpoint(s)
 
The primary endpoint is model-based exposure (<math>\text{AUC}_{\tau,ss,\text{combined}}</math>) of selexipag and ACT-333679, corrected for their potency, determined during the 12-week up-titration period.

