	
All analyses of safety variables will be carried out descriptively using the Safety Analysis Set, consisting of all treated participants, and will be performed as follows:
 
 
• in the overall population.
 
• by iMTD dose groups.
 
• by age cohort.
 
 
The number and percentage of participants with at least one TEAE / TESAE / AE leading to study treatment discontinuation will be described by system organ class (SOC) and preferred term (PT) up to EOT + 3 days, and separately for the up-titration period (until Week 12) and the maintenance phase (> Week 12 until EOT + 3 days).
 
The same analysis will be performed according to the maximum intensity of reported AEs and their relationship to the study drug.
 
The number and percentage of treatment-emergent deaths will be described by SOC and PT up to EOT + 3 days.
 
For each laboratory and ECG variable, the number and percentage of participants with at least one treatment-emergent marked abnormality will be summarized up to EOT + 3 days.
 
Vital signs and sexual maturation variables will be summarized over time up to EOT + 3 days, using descriptive statistics for continuous variables.

STUDY COMMITTEES
	
An IDMC has the overall responsibility for safeguarding the interests of participants by monitoring safety data obtained in the study and by making appropriate recommendations based on the reported data, thus ensuring that the study is being conducted with the highest scientific and ethical standards. The PK results of the interim analyses (after completion by Cohorts 1 and 2, and final PK results of all three cohorts) will be provided to the IDMC for review, if requested by the committee. The IDMC will be fully operational prior to enrollment of the first participant into the study. The

	composition and operation of the IDMC is described in the IDMC charter.
--	---

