### 3.1.1 Study periods

The study consists of the following consecutive periods:

**Screening period:** Lasts up to 42 days; starts with the signature of the informed consent form (ICF) and ends with the administration of the first study treatment dose.

**Treatment period:** Starts from the first dose of study treatment at Baseline/Enrollment visit and ends on the day of the last dose of selexipag (EOT). This includes:

- **Up-titration period:**

From the first dose of study treatment until the participant reaches their iMTD. This period is estimated to last up to 12 weeks.

Details of up-titration are described in Section [5.1.4](#).

- **Maintenance period:**

**After Week 12:** The participants will continue study treatment at the same dose up to Week 16.

**After Week 16:** Study treatment will continue as long as it remains beneficial for the participant, but up to a maximum of 5 years after last participant first visit [see Section 3.1.2 for details].

**EOT visit:** This visit should be conducted within 1 week of the last dose of study treatment.

[figure not shown]
**Safety Follow-up period:** Starts on the day after the last dose of study treatment and ends about 30 days thereafter with a phone call that will serve as the End-of-Study (EOS).

The visit schedule and protocol-mandated procedures will be performed according to the table of assessments [Table 4, Table 5] and are described in Section 7.

The overall study design is depicted in Figure 2.

Confidential

Figure 2 Study design

b.i.d twice daily; D day; eq. equivalent; EOS End of Study; EOT End of Treatment; FU follow up;  
 M month; q every; V visit; W week.  
 Equivalent (eq.) refers to the equivalent dose according to the body weight category as described in Section 5.1.4.

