The body weight category, starting dose, and up-titration scheme determined at Baseline/Enrollment will be kept unchanged until Week 16. After Week 16, if the body weight category of the participant changes, study drug can be up-titrated further or down-titrated to the corresponding dose level of the next body weight category, as deemed appropriate by the investigator (if dose levels overlap between body weight categories, the dose level may also remain stable).

In addition, irrespective of whether the body weight category changes or not, after Week 16 the investigators will be allowed to change the participant's study medication dose further if needed (up to the maximum allowed dose based on body weight category).

If a participant has tolerability issues and experiences adverse reactions reflecting the mode of action for selexipag [see Section 5.1.10], the dose can remain the same without further up-titration (pause in up-titration). Up-titration can be resumed after the pause, or the dose can be reduced to the previous dose level. The decision to pause up-titration, to up-titrate or down-titrate study drug, or to permanently discontinue study drug treatment will be based on the investigator's medical judgment [see Section 5.1.10].

If a dose of selexipag is missed, participants should take a dose as soon as possible unless the next dose is within the next 6 h. During the up-titration period, the investigator / site staff must ensure that PK samples are collected after 3 days at the same dose and using the same mode of administration.

At any time during study treatment, study drug interruptions (eg, missed doses for any reason) of 3 days or more will require a new up-titration according to the scheme from Day 1.

All selexipag dose changes and reasons for dose interruptions must be documented in the eCRF.

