#### **5.1.10 Study-specific criteria for pause in up-titration / interruption / premature discontinuation of study treatment**

##### **A) Tolerability issues / AEs**

Adverse reactions associated with the mode of action of selexipag have been observed frequently, in particular during the phase of individualized dose titration. These include: headache, diarrhea, nausea and vomiting, jaw pain, myalgia, pain in extremity, arthralgia, and flushing. In adult participants with PAH, these effects were usually transient or manageable with symptomatic treatment. Gastrointestinal events have been observed to respond to antidiarrheal, antiemetic, and anti-nausea medicinal products and/or medicinal products for functional gastrointestinal disorders. Pain-associated events have frequently been treated with analgesics (such as paracetamol).

However, if a participant reaches a dose that cannot be tolerated, the investigator should follow the instructions given in Section 5.1.4.

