##### 10.3.5.1 Treatment-emergent adverse events

The number and percentage of participants with at least one TEAE / TESAE / AE leading to study treatment discontinuation will be described by system organ class (SOC) and

---

 The geometric mean of  $t_{max}$  and its 95% CI will not be calculated.

preferred term (PT) up to EOT + 3 days, and separately for the up-titration period (up to Week 12) and the maintenance phase (> Week 12 up to EOT + 3 days).

The same analysis will be performed according to the maximum intensity of reported AEs and according to the relationship to the study drug.

Listings will be provided for all reported AEs, including SAEs. In addition, separate listings will be provided for all AEs leading to premature discontinuation of study drug, and for all AEs leading to death.

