2.2. Study Analysis Periods

For each dosed participant, the screening, treatment and follow-up phases of the study will be structured as following:

Table 3: Study periods definition

Period	Period Start	Period End
Screening	Starts with the signature of the informed consent form (ICF), may be as early as Day -42	Prior to the administration of the first study treatment dose
Treatment		
Up-Titration	the first dose of study treatment	the participant reaches their iMTD (iMTD for each participant is determined at Week 12, or EOT + 3 days in case of premature treatment discontinuation before Week 12)
Maintenance after Week 12 to 16 (continue treatment at same dose)	Day of Up-Titration end plus 1.	Up to Week 16 or EOT + 3 days in case of premature treatment discontinuation before Week 16

Period	Period Start	Period End
Maintenance after Week 16	Day of Week 16 visit plus 1	EOT (up to 5 years after last participant, first visit)
EOT visit	This visit should be conducted within 1 week of the last dose of study treatment. The participant will then enter the Safety follow-up period.	
Safety follow-up	Day after EOT	EOS - Day of Safety follow-up Phone call (about 30 days after last dose)

In case a participant drops out during a treatment period, the participant will have a Follow-Up period after the last applicable treatment period only if a Follow-Up visit was performed.

Each of these analysis periods is associated with a treatment. Treatments for the Screening and Follow-Up periods are defined as ‘None (screening/follow-up)’, respectively.

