4.1. Adverse Events

Adverse Events and Treatment-Emergent Adverse Events

- Summaries of below adverse event categories will be summarized according to the study periods *Up-Titration*, *Maintenance after Week 12*, *Maintenance after Week 16* as defined in [Table 2](#).
- All reported adverse events with onset following the start of study treatment, or pre-existing conditions that have worsened since baseline, will be defined as treatment-emergent (TEAE) and will be included in the analysis. TEAEs will be recorded up to EOT + 3 days.
- AEs will be analyzed by period, and the start or worsened date-time of the AEs will be used to determine the period the AE falls in.
- For each TEAE, the percentage of participants who have experienced at least 1 occurrence of the given event will be summarized by system organ class, preferred term, and age cohort.
- TEAEs will be tabulated by severity and relationship and will be summarized by system organ class, preferred term, and age cohort.
- Serious AEs and AEs occurring up to EOT + 3 days that lead to death, hospitalization, treatment discontinuation, dose reduction/interruption will be tabulated and listed.
- AEs that occur during screening and that start prior to first dosing will be included in data listings only.
- All reported adverse event terms will be coded with the latest available MedDRA dictionary version.
- COVID-19 related AEs will be listed.

Adverse Events of Special Interest(AESI):

Adverse events of special interest (AESI) for this study have been defined in [Appendix 2](#).

For each AESI category, the percentage of participants who have experienced at least 1 occurrence of the given event will be summarized by system organ class, dictionary derived preferred term, and age cohort.

AESIs will be also tabulated by severity and will be presented by treatment periods, age cohort, body weight and overall. AESIs will also be summarized by relationship to the study drug.

Number of recurrent AESIs will be counted as the total number of occurrences of any TEAEs, i.e., multiple occurrences for the same preferred term for the same participant will be counted multiple times. Average annualized event rate will be calculated as follows:

- 1) Calculate total number of recurrent TEAEs.
- 2) Calculate participant-years of treatment duration (sum of individual participant time-years in a treatment group)
- 3) Average annualized event rate = (total number of recurrent TEAE) / (subject-years of treatment duration)

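### Adverse event periods are cut by calendar date, so reactions that start during a repeat titration or after a late dose increase are counted under maintenance

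*Protocol*

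**What the plan says.** **Period split in the protocol.** Section 10.3.5.1 describes participants with at least one event up to 3 days after end of treatment, and also "separately for the up-titration period (up to Week 12) and the maintenance phase (> Week 12 up to EOT + 3 days". The synopsis has the same split: "separately for the up-titration period (until Week 12) and the maintenance phase".

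**Period split in the SAP.** Table 3 in section 2.2 uses three treatment periods: up-titration, maintenance from Week 12 to 16 (labelled as treatment at the same dose), and maintenance after Week 16. It words the end of up-titration as reaching the individual maximum tolerated dose (iMTD), but adds that the "iMTD for each participant is determined at Week 12", so the cut is in practice Week 12. Section 4.1 states that "the start or worsened date-time of the AEs will be used to determine the period the AE falls in".

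**Dosing that does not follow those dates.** Protocol section 5.1.4 says that interruptions, at any time during study treatment, "of 3 days or more will require a new up-titration according to the scheme from Day 1". The synopsis says that "after Week 16 the investigator will be allowed to change the" dose further, up to the maximum for the weight category, whether or not that category changes.

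**Two further statements that bear on the point.** Protocol section 3.1.1 defines up-titration by dose, not date: "From the first dose of study treatment until the participant reaches their iMTD". Section 5.1.4 also says that the dose fixed at Week 12 should stay unchanged until Week 16.

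**The concern.** Safety and tolerability is the secondary objective. Section 5.1.10 of the protocol says that reactions linked to the drug's mode of action are frequent, "in particular during the phase of individualized dose titration". A table headed maintenance is naturally read as describing a child on a settled dose, and the SAP's label for Weeks 12 to 16 says as much.

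A child who restarts from Day 1, or whose dose is raised, is being titrated again. If a headache or vomiting begins in those weeks, only its date decides the column, and after Week 12 that column is maintenance. No passage in either document assigns this time back to titration or flags the event. The contrast between titration and stable dosing is blurred, most of all for the prostacyclin-associated reactions, which the SAP summarises by study period.

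**Working it through.** The plan states no figure that depends on the split, so there is nothing to reproduce. The check uses the schedule, the period definitions and a labelled illustration.

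**Inputs.** Eight dose levels in weekly steps, with level 8 from the evening of Week 7 (Protocol Tables 1 to 3). Period boundaries at Weeks 12 and 16 (SAP Table 3). About 20 children per cohort and 60 in all (Protocol section 3.1). The share of children who restart or are raised after Week 12 is not in the documents.

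**1. Which tables can be reached.**

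| Episode | SAP Weeks 12–16 | SAP after Week 16 | Protocol pooled maintenance |
|---|---|---|---|
| Restart after an interruption in Weeks 12–16 | yes | yes, if it runs past Week 16 | yes |
| Restart after Week 16 | no | yes | yes |
| Dose increase after Week 16 | no | yes | yes |

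**2. Length of a restart.** Level 1 to level 8 takes 8 − 1 = 7 weekly steps; the Week 12 to 16 window lasts 16 − 12 = 4 weeks. A restart at Week 13 that goes to the top reaches it at 13 + 7 = Week 20: 3 weeks fall before Week 16 and 4 after. A child who stops at a lower level takes fewer weeks.

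For a restart at Week r before Week 12, r + 7 exceeds 12 when r > 5, and r + 7 reaches 16 when r ≥ 9. On the schedule alone, such restarts would run into Weeks 12 to 16 in part or in full. This holds only if the re-titration rule prevails over the unchanged-dose rule, and the documents do not say which does.

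**3. Size per child.** 1/20 = 5 points within a cohort; 1/60 = 1.7 points overall. These are ceilings: the child must have the reaction in that time and no other such event in the same period.

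**4. Illustration.** Let p be the true incidence on a stable dose, f the share who restart or are raised after Week 12, and q the chance of the reaction in that repeat titration, independent of p. Then

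observed maintenance incidence = p + f × q × (1 − p).

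All inputs here are assumptions: p = 10% or 32%, q = 33% or 65%, f = 5% to 30%. Of these, 65% and 32% are the adult headache rates on selexipag and placebo in Protocol section 1.2.3.4.2, and 33% is their difference. They cover the whole adult trial and only set a scale.

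- Smallest: 0.05 × 0.33 × (1 − 0.32) = 0.011, or 1.1 points (0.2 of 20 children).
- Largest: 0.30 × 0.65 × (1 − 0.10) = 0.1755, or 17.6 points (3.5 of 20 children).

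**5. A pull the other way, on a different measure.** Assignment by onset leaves out of maintenance any reaction that began before Week 12 and persists without worsening. If a share g = 10% to 50% of stable-dose events were of this kind, a reader who takes the table as symptom burden would see it understated by p × g, from 0.10 × 0.10 = 1.0 point to 0.32 × 0.50 = 16.0 points.

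**6. The label also errs before Week 12.** A child who reaches level 8 on schedule at Week 7 and tolerates it has 12 − 7 = 5 weeks at the top dose counted as up-titration, although section 3.1.1 would end up-titration when the iMTD is reached.

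**The case against.** The strongest reply has four parts.

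- **The SAP already separates the periods.** Only Weeks 12 to 16 carry the same-dose label. The later period openly allows dose changes, so its table describes flexible long-term dosing. This stands in part: a post-Week 16 increase cannot affect the Week 12 to 16 table. A restart within Weeks 12 to 16 can, and the protocol's own maintenance phase pools everything after Week 12.
- **The unchanged-dose rule.** A child who restarted before Week 12 may have the Week 12 dose recorded as iMTD (SAP section 3.6) and held. A reader might infer from the schedule alone that restarts from about Week 5 spill into Weeks 12 to 16. The documents do not support that without first settling which rule governs.
- **Direction.** A reader might infer that maintenance tolerability will look worse than it is. For onset incidence, this mechanism alone can only raise the figure. For total symptom burden, persisting reactions pull the other way, and the net direction is not determined.
- **Other outputs.** Whole-treatment tables are unaffected by the cut; adverse events and the treatment log are listed; and annualized rates are planned for events of special interest, which include prostacyclin-associated reactions. These help someone tracing individual cases. But the annualized rate is defined over total treatment duration, so no planned table separates titration from stable dosing.

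A weight-category change is also not always an increase: section 5.1.4 allows down-titration, or no change where dose levels overlap.

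**Conclusion.** The point holds in a limited form. Both documents assign events by date with no link to dose history, and a plan followed as written will place reactions from a mandated restart, or from a permitted late increase, under a maintenance heading. This can raise onset incidence in the tables marked in step 1.

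The size cannot be stated. The range of 1.1 to 17.6 points rests wholly on assumed inputs and is not an estimate for this trial. The firm statement is the ceiling of 5 points per child with 20 in the denominator. It would be tempting to multiply that ceiling by a guessed number of restarts, but the documents give no frequency, and many such children may already have a maintenance event, since treatment may continue until 5 years after the last participant's first visit.

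The analysis is descriptive, and no primary pharmacokinetic result, error rate or sample size depends on it. The change is worth making for the secondary objective, but the calendar tables need not be demoted.

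**What to change.** 1. **Keep the calendar-period tables** and add to SAP section 4.1 supplementary tables of treatment-emergent events and prostacyclin-associated reactions by actual dosing phase, derived from the Study Treatment Log.
2. **Define the phases for analysis only.** Titration time runs from the first dose, from any restart after an interruption of 3 days or more, and from any dose increase, until a pre-stated window after the last increase (for example 7 days, one step in Tables 1 to 3). All other on-treatment time is stable dosing. State where an event with onset during the interruption itself belongs.
3. **Report events per participant-year in each phase**, because a child can move in and out of titration.
4. **Reconcile the definitions.** Align the iMTD-based end of up-titration in Protocol section 3.1.1 with the Week 12 cut in the synopsis, section 10.3.5.1 and SAP Table 3. Reconcile the unchanged-dose statement for Weeks 12 to 16 with the re-titration statement, both in section 5.1.4. Which clinical rule governs is for the sponsor to settle.
5. **Correct the cross-reference** in SAP section 4.1, which points to Table 2 for the periods; they are in Table 3.

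The cost is SAP wording and some programming. Dose changes and interruptions are already recorded in the eCRF (Protocol sections 5.1.4 and 5.1.8), and SAP section 3.5 already draws on the log. The downside is that phases become intermittent within a child, so percentages alone will not suffice.

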## PROTOCOL

### 1 BACKGROUND

#### 1.1 Indication

Pulmonary arterial hypertension (PAH) in children.

##### 1.1.1 Definition and diagnosis

PAH is a rare, progressive and eventually fatal disease, characterized by vasoconstriction and progressive remodelling of pulmonary arteries leading to increased resistance to blood flow in the pulmonary circulation, right ventricular failure, and death. With regards to the definition, pathophysiology, symptoms, and response to PAH-specific medicines, PAH disease in children shares similarities with adult PAH [[Barst 2011](#)].

The definition of PAH in adults and children is the same and is based on pulmonary hemodynamics measured by right heart catheterization (RHC): a mean pulmonary artery pressure (mPAP)  $\geq 25$  mmHg at rest demonstrates pulmonary hypertension (PH). In patients with PAH, the PH is pre-capillary; thus, they have a normal pulmonary artery wedge pressure (PAWP)  $\leq 15$  mmHg and an elevated pulmonary vascular resistance (PVR)  $> 3$  Wood units (WU) (mmHg/L·min) [[Hoeper 2013](#), [Ivy 2013](#)]. In children, PVR index (PVRi) is used instead of PVR in order to account for growth; PAH is defined as  $PVRi > 3 \text{ WU} \times \text{m}^2$  [[Ivy 2013](#), [Abman 2015](#), [Hansmann 2016](#)].

$$PVRi [\text{WU} \times \text{m}^2] = \frac{\text{mPAP} [\text{mmHg}] - \text{PAWP} [\text{mmHg}]}{\text{cardiac index} [(\text{L}/\text{min}) / \text{m}^2]}$$

$$\text{cardiac index} [(\text{L}/\text{min}) / \text{m}^2] = \frac{\text{cardiac output} [\text{L}/\text{min}]}{\text{body surface area} [\text{m}^2]}$$

A PAH diagnosis can be confirmed only if elevated left heart pressures are excluded as a reason for PH. PAWP is used for this purpose as a surrogate for directly measured left atrial pressure (LAP) [[Galiè 2015](#)]. In the absence of mitral stenosis, left ventricular end diastolic pressure (LVEDP) can also be used as an alternative surrogate for LAP [[Grignola 2011](#), [Takala 2003](#)].

Beyond the neonatal period, the pathology of pulmonary vascular disease is generally the same across all age ranges. The histopathological findings seen in adults with PAH are also observed in children. Both populations have vascular and endothelial dysfunction, and present at diagnosis with elevations in PVR and pulmonary artery pressure [[Barst 2011](#)]. The distribution between etiologies in pediatric PAH is different to that of adults. There are no indications from clinical experience that this translates into differences in response to PAH-specific medicines.

